**Table 7. PROJECT TIMELINE**

| Months  | Year 1 |      | Year 2 |      | Year 3 |      | Year 4 |      |
|---|--------|------|--------|------|--------|------|--------|------|
|   | 1-6    | 7-12 | 1-6    | 7-12 | 1-6    | 7-12 | 1-6    | 7-12 |
| Submit IRB protocol for full review                   | X      |      |        |      |        |      |        |      |
| Datstat refines computerized GMI PFR/troubleshoot     | X      |      |        |      |        |      |        |      |
| Update/refine GMI treatment manual                    | X      |      |        |      |        |      |        |      |
| Hire project coordinator and research assistant       | X      |      |        |      |        |      |        |      |
| Hire study therapists                                 | X      |      |        |      |        |      |        |      |
| Compile study assessments & process measures          | X      |      |        |      |        |      |        |      |
| Co-I [name] meet for cost estimation           | X      | X-IP | X      | X    | X      | X    | X-IP   |      |
| Conduct Veteran & staff stakeholder focus groups      | X      |      |        |      |        |      | X      |      |
| Develop & conduct GMI Training for therapists         | X      |      |        |      |        |      |        |      |
| Establish/conduct therapist fidelity monitoring       | X      | X    | X      | X    | X      | X    |        |      |
| Develop quantitative process assessments & monitoring | X      |      | X      |      | X      |      | X      |      |
| Participant consenting/recruitment/enrollment         |        | X    | X      | X    | X      | X    |        |      |
| Establish project database                            | X      |      |        |      |        |      |        |      |
| Conduct participant F/U assessments                   |        | X    | X      | X    | X      | X    | X      |      |
| Conduct data entry and data checks                    |        | X    | X      | X    | X      | X    | X      |      |
| Update GMI adherence/competence manual                |        | X    |        |      |        |      |        |      |
| Train raters on therapist adherence/competence        |        |      |        |      | X      |      |        |      |
| Raters rate therapy tapes using MITI                  |        |      |        |      | X      | X    |        |      |
| Meet with economist for cost estimation               | X      | X    | X      | X    | X      | X    | X      |      |
| Meet with statistician for analyses                   |        | X    |        | X    |        | X    | X      | X    |
| Statistical analyses for main outcomes                |        |      |        |      |        |      | X      | X    |
| Manuscript preparation/submission                     |        |      |        |      |        |      | X      | X    |

\*IP = In Person

## PROTECTION OF HUMAN PARTICIPANTS

### 1. Risks to the Participants

#### A. Human Participants Involvement and Characteristics

The PI and Co-Is have all completed the University of Miami computer-based CITI Human Participants Research Education Course. One hundred eighty-six (186) ethnically/racially diverse male and female Veterans with current alcohol/drug dependence or abuse will be recruited over a 30-month period. Participants with a non-substance related major DSM-IV-TR Axis I disorder (e.g., major depressive disorder, bipolar disorder, anxiety disorder, schizophrenia, schizoaffective disorder, psychotic disorder) will be eligible.

Additional inclusion and exclusion criteria are described below.

#### Inclusion Criteria

- 1) Men and women Veterans currently in HUD-VASH or GPD, newly entering the program but not yet housed, or Veterans on the HUD-VASH interest (wait) list.
- 2) Able to comprehend English.
- 3) Meets DSM-V criteria for a current substance use disorder and have used substances in the 30 days prior to treatment entry. Participants on medications targeting their substance use must be stabilized on medications for at least 2 weeks before therapy initiation.
- 4) May meet criteria a mood, anxiety or other psychiatric disorder. Participants on maintenance medications for a mood or anxiety disorder must be stabilized on medications for at least 2 weeks before therapy initiation.
- 5) Able to adequately provide informed consent and function at an intellectual level sufficient to allow accurate completion of all assessment instruments.
- 6) Willing to commit to 4 group therapy sessions, baseline, 1, 3, and 6 month follow-up assessments.

#### Exclusion Criteria

- 1) Active suicidal or homicidal ideation with a plan as this is likely to require hospitalization or other interventions that could interfere with study participation.
- 2) Unstable psychiatric condition that is likely to require hospitalization or other interventions that would interfere with study participation.
- 3) Unstable medical condition or one that may require hospitalization during the course of the study.

#### B. Sources of Materials

1. Research material obtained from individual participants includes self-report questionnaires, structured interviews with study personnel, taped therapy sessions as well urine and breathalyzer samples.
2. The research material will be obtained specifically for research purposes. Written research material obtained will be stored in a locked file cabinet in an office that is locked when not in use. The master list of participants linking study numbers to any source identifying information will be in a separate locked file cabinet at the Charleston VAMC in the PI's office (Room A562a). Urine samples will be discarded after results are documented.
3. Therapy sessions will be digitally audio-recorded to be used for supervision and adherence monitoring. They will be transferred electronically and stored behind the VA firewall and accessible only to project staff.

#### C. Potential Risks

Risks to the patients include feeling distress being interviewed regarding substance use and other sensitive information, adverse events related to the study intervention (see adverse event definitions below) and risk of loss of confidentiality regarding the information obtained during the assessment and follow-ups and taped therapy sessions. Potential psychological risk of the treatment includes exacerbations of distress and increase in substance use during the assessment and/or treatment sessions.

#### **2. Adequacy for Protection Against Risk and Harm to Participants**

## A. Recruitment and Informed Consent

Participants will be recruited from the Charleston (VAMC) HUD-VASH and GPD housing programs. Housing or project staff (Note: The PI, [name], works in the housing program and she is considered housing staff) will invite patients to inform them about the study and elicit interest. Interested potential participants will be screened for major inclusion/exclusion criteria including substance use and psychiatric/health/medication status. Prior to any study procedures being performed, the Institutional Review Board (IRB) approved informed consent will be obtained by research staff trained in informed consent procedures. Informed consent will be collected at the study research offices, in a private and interruption-free environment. Explanation of the informed consent document will include a detailed description of the study in easy to understand detail with the participant, along with statements regarding participants' rights to withdraw from the procedure at any time without consequences. The participant will be asked to read the document and if he or she has any questions, they will be answered prior to participant signature. Consent will be documented by the date and signature of the participant on an informed consent agreement and by the date and signature of the individual obtaining the consent. A HIPAA authorization form will also be signed, and copies of both documents will be provided to the participant. Potential participants may decide to discuss participation with their families and/or significant others prior to making a decision to sign consent.

## B. Protection against Risk

All investigators and project personnel have completed a certified program of instruction in the protection of human participants in research, the University of Miami CITI course. These courses on the responsible conduct of research and the protection of human research participants will be completed on a regular basis, in compliance with MUSC institutional regulations. All research activity, informed consents and continuing reviews will be reviewed by MUSC's IRB in compliance with 45CFR46 before the research is started and continuing review will occur annually. The research staff will ensure that all information needed for the continuing review is at the IRB in accordance with IRB requirements.

We will take careful precautions to maintain confidentiality for all participants, using procedures we have used with similar previous studies. All data will be stored in a confidential manner (i.e., in locked files in the Study Coordinator's research office and behind the VA computerized firewall) so as to protect the confidentiality of participant information. Access to research records (paper and computerized) will be restricted to the project staff. Specifically, access to de-identified study data will be limited to named project investigators, the Study Coordinator and MUSC IRB or R&D audit personnel. Binders with study data will have a study number that will be kept locked separately from any source documents with identifying information. The master list of participants linking study numbers to any source identifying information will be kept in a separate locked file cabinet in the PI's office at the Charleston VAMC. When study results are published or presented, only aggregate reports of the results will be used and participants' identity will not be revealed. All analyses will be conducted on de-identified data only.

Therapy sessions will be digitally audio-recorded to be used for therapist supervision and adherence monitoring. They will be transferred electronically and stored behind the VA firewall and accessible only to project staff.

Exclusion criteria are crafted to exclude potential participants at higher risk for adverse effects, including those with co-occurring medical or psychiatric disorders where they may be more likely not to benefit from the intervention and/or to be hospitalized during the course of the study. The informed consent document specifically reviews potential psychological distress as a potential outcome of participation.

Measures to avoid potential risk associated with psychological distress/substance use include exposure to the intervention that includes non-judgmental therapist feedback, imparting autonomy (e.g., participants are free to decide what they want to do about their substance use), and reduction of substance use through enhancing participant motivational change talk. Additional measures include informing participants that they are free to terminate treatment sessions at any time. Risks associated with assessment include the possibility that participants might be upset by questions pertaining to their emotional functioning. Some participants might be offended by detailed questions about health status and impairment. Our past research suggests that data collection using many of these measures can be conducted without undue psychological distress or exacerbation

of symptoms among adult participants. This experience includes research with younger and older adult Veterans, victims of violence, and substance abusing individuals asking questions about similar topics with general population samples.

Social risks are present if another person or parties observe participants attending treatment or learn by other means of participants receiving treatment. Participants will not be overtly identified as research participants or participants for psychological intervention.

In the event participants experience extreme psychological distress secondary to participation, they will be encouraged to talk with the Principal Investigator (PI) or the Co-I's. In addition, they will have access to the VAMC treatment services. Any such adverse effects noted by any project personnel in response, or in potential response to any project intervention, assessment protocol, or study involvement will be immediately reported to the PI and Co-I's. Participants will also be given the PI's name and telephone number and the Study Coordinator's contact information. Moreover, if research or clinical staff believes that a participant is significantly distressed by participation, the PI will be notified and will contact the participant to assess distress and assure participant safety. If called by participants, the PI will attempt to address all participant concerns and if indicated, set up an alternate referral for counseling for those who desire it from outside the project.

If at any point during the assessment, treatment or follow-up period, participants are in need of medical management, psychiatric consultation or psychiatric hospitalization, they will be evaluated and if indicated, referred to a more intensive level of treatment. If a participant becomes suicidal, emergency psychiatric assessment will be arranged. The participant will be closely monitored clinically until they are no longer suicidal or an appropriate safety plan is in place. A procedure for clinical deterioration has been established based upon our experience with previous studies. Therapists will be instructed to use their best clinical judgment regarding emergencies and inform the PI, Co-I's or PC as soon as possible. In addition to relying on clinical judgment on the part of the treating therapist(s) who are experienced with this population, substance use, and psychiatric indices will also be monitored at follow-ups (TLFB, BSI) in order to detect any symptom worsening requiring further evaluation. Additionally, participants are advised to observe any signs of worsening substance use, depression and anxiety symptoms and to discuss these with their therapist or other project staff. If in the clinical judgment of the therapist in collaboration with the PI/Co-I's, it is determined that the participant symptoms are worsening at any point during study participation, appropriate referrals will be made. These decisions will be dealt with in training and supervision of project staff and will be monitored carefully.

Patients will be terminated from the study and referred for more intensive treatment if there are:

- a. Increases in alcohol or drug use leading to the need for a more intensive level of care (i.e., medical detoxification, inpatient).
- b. Active suicidal or homicidal ideation.
- c. Inability to manage psychiatric symptoms within the inclusion/exclusion criteria of the study (i.e., need for the initiation of maintenance psychotropic medications; development of psychosis). If it is determined, based on clinical criteria, that a participant needs to be started on maintenance medications for anxiety, mood or psychotic symptoms during the course of the study, they will be discontinued from the treatment trial.

At the VAMC, there is a well-established protocol for emergency psychiatric evaluation, crisis intervention and/or psychiatric hospitalization for suicidal, homicidal, psychotic or other acutely distressed patients. Immediately on detection of these needs, the PC, RA, or research therapist will contact the PI or on-site Co-I's to review the patient's situation. If appropriate, PI or on-site Co-I's will personally evaluate the patient. During evenings or weekends, the PI/Co-I's will be on call for emergencies. At these times, acutely distressed patients will be instructed to go to the psychiatric emergency room for evaluation by a psychiatric resident. The PI/Co-I's will notify the resident in advance of the patient's situation. Acute psychiatric hospitalization is available for emergencies.

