patients and collaterals were interviewed at 1 and 3-month follow-up. Three main outcomes of the pilot study showed that: 1) GMI reduced the number of inpatient hospital detoxification re-admissions after initial hospitalization compared to ST: GMI participants were re-admitted to inpatient detoxification fewer times (GMI: 6.8%; ST: 25.6%;  $p = .03$ ) during the 3-month follow-up period; 2) Participants in GMI attended more outpatient aftercare treatment sessions compared to participants in ST ( $M=5.7$  [SD=6.7] vs.  $M=2.5$  [1.9];  $p=.001$ ) and attended more 12-Step or AA/NA self-help sessions ( $M=21.7$  [18.8] vs.  $M=6.8$  [6.8];  $p<.01$ ) by 3-month follow-up; and 3) GMI was associated with reduced substance use: Participants in GMI drank less alcohol (measured in standard ethanol content units), compared to their counterparts in ST by 3-month follow-up ( $M=117.3$  [182.8] vs.  $M=262.3$  [312.9],  $p=.04$ ), engaged in less binge drinking ( $M=4.6$  [3.2] vs.  $M=13.9$  [10.5],  $p=.001$ ) and had fewer days of illicit drug use ( $M=5.2$  [7.2] vs.  $M=13.0$  [12.0];  $p=.01$ ) at 1-month follow-up. A smaller *proportion* of GMI participants reported binge drinking (34.1% in GMI vs. 55.8% in ST,  $p = .02$ ) at the 3-month follow-up.

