**C5. Randomization Procedures.** *Participants will be assigned to GMI or CT using a block randomization procedure successful in shortening the amount of time needed to fill a group. This procedure was successfully utilized in [name] CDA. In this procedure, a set of consecutively admitted participants will be assigned to the same treatment condition with 'recruitment week' being the unit of randomization (i.e., recruitment weeks themselves are randomized). A computer randomizes recruitment weeks; therefore, all participants entering the study in a treatment week enter the same treatment condition. Since session attrition occurs infrequently (i.e., some participants may elect to not attend a particular session for various reasons) and is typically no more than 1 to 2 absent individuals, we will recruit at least 6 participants per workshop to ensure that there will be enough attendees present. Thus, we anticipate between 3 to 6 participants will attend any one session; providing a maximum of (up to) 62 workshops each containing four sessions for a maximum total of 31 workshops in GMI (124 sessions) and 31 workshops in CT (124 sessions). Once a Veteran is randomized he or she will be entered into the study and included in intent-to-treat analysis. We will track session attendance. Should there be a difference on group member attendance between treatment conditions, we will account for within session correlations of outcome by including random effects corresponding to the clusters.*

**C6. Description of Proposed Novel Intervention (see appendix for GMI treatment manual).** GMI & CT group sessions will take place in various community locations (e.g., HUD-VASH apartment complexes/GPD residential programs [e.g., Charleston Vets]).

**Group motivational Interviewing (GMI):** Following randomization, participants will be scheduled with their study therapist (see therapist training in section C8) in a closed group. GMI participants will receive four structured,

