### **C7. Description of Comparator/Control Conditions**

Control Treatment Condition (CT): *Participants in CT will attend four sessions equal in time and length to GMI (i.e., 90 minutes) and will involve the following topics: A popular ‘box activity’: participants will anonymously write evocative questions on slips of paper involving their personal concerns that are placed in a box and, when randomly selected, opened for group discussion (e.g., “How do I talk to my family about my alcohol problem?”), money management with feedback (2 sessions), psychoeducation about substance use, and cooking-home maintenance.*

Session timing: *We will aim to complete GMI and CT sessions over the course of one week (Tuesday – Friday) when feasible and practical. Our session timing aim is based on evidence from the PI’s prior work, given her success with this approach in her pilot and CDA, whereas the efficacy of GMI delivered over a longer period of time is less certain. We plan to make every effort to complete group sessions on 4 consecutive days, as that approach was used in prior successful efforts. However, at times, we may encounter participants within a particular group who have limited availability to attend consecutive sessions within one week; thus, we will make reasonable efforts to reduce barriers to attend sessions (e.g., holding sessions every other day).*

Description of Booster Session: *Participants in both GMI and CT will be asked to attend a 1 hour booster session 2 months after they receive the intervention to maintain consistency with the treatment, reduce participant drop out (as there are no formal assessments being conducted at the second month) and to increase potential to motivate and enhance proactive behaviors among group members to engage in the therapeutic material discussed in both GMI and the TCC interventions.*

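### Deteriorating participants are terminated from the study with no statement that the month 1, 3 and 6 assessments continue; unrecorded terminations that differ by arm would bias the substance-use comparison

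*Combined protocol and SAP*

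**What the plan says.** Protection of Human Participants, section 2B, gives the rule: "Patients will be terminated from the study and referred for more intensive treatment if there are". Three triggers follow:

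- (a) "Increases in alcohol or drug use leading to the need for a more intensive level of care", meaning detoxification or inpatient treatment;
- (b) active suicidal or homicidal ideation;
- (c) psychiatric symptoms that can no longer be managed within the eligibility criteria, including psychosis or the need to start maintenance medication. For the medication case the text says "they will be discontinued from the treatment trial".

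No time limit is attached to the rule. The preceding paragraph opens with "If at any point during the assessment, treatment or follow-up period", but those words govern evaluation and referral. The same paragraph has substance use (TLFB) and symptoms (BSI) checked at follow-up visits to detect worsening.

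On the analysis side, C5 says "Once a Veteran is randomized he or she will be entered into the study and included in intent-to-treat analysis", and C12 makes the ITT set primary. C12a relies on GLMMs valid under MAR. It adds an ITT versus per-protocol comparison, a logistic model for missingness, documented reasons, a general intention to correct for informative drop-out, and a missing-equals-failure worst case for dichotomous outcomes, illustrated with non-drinking days. C12d names month 1 as the primary time point. No section says whether assessments or CPRS encounter counts continue after termination.

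**The concern.** Trigger (a) is a deterioration in a primary outcome domain (H1, substance use). If termination also ends assessment, the participant stays in the ITT set with earlier data only, and the outcomes lost are the bad ones.

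A MAR model fills the gap from what was recorded earlier. TLFB is a retrospective calendar, so the next visit would have captured the drinking that led to an admission; cancelling that visit hides it. After the week-2 sessions, scheduled contact is limited to visits at weeks 4, 12 and 24 and one booster ("Participants in both GMI and CT will be asked to attend a 1 hour booster session 2 months after they receive the intervention"), so a trigger can fall between visits.

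At stake is the estimated substance-use effect, mainly at months 3 and 6 and in the trajectory comparison. Outcomes never collected cannot be recovered by analysis.

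**Working it through.** **1. The plan's own figures (C11).** 65 per group with 30% drop-out: 65 / 0.70 = 92.9, so 93 per group, as stated. For power, the SD of the difference is not given, so 0.4 drinks is read as 0.40 SD. With m measurements and correlation 0.5, SE = sqrt(2 × [(1 + (m - 1) × 0.5) / m] / 65). For m = 3, SE = 0.143 and power is 79.8%. For m = 4 (counting baseline), SE = 0.139 and power is 82.2%, near the stated 83%.

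**2. Direction.** Let p be the proportion of an arm missing through termination, and δ how much worse those participants truly are than the MAR prediction. With negative values favouring GMI:

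estimated difference = true difference + p(CT) × δ(CT) - p(GMI) × δ(GMI).

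Simulated month-1 results with a soft (logistic) trigger on current, unrecorded use and true difference -0.40 follow this, taking one δ for both arms:

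- More in CT (5.8% v 2.1%): estimate -0.375, implying δ = 0.025 / 0.037 = 0.68. Check: -0.40 + 0.058 × 0.68 - 0.021 × 0.68 = -0.375.
- More in GMI (10.4% v 5.8%): estimate -0.429, implying δ = 0.029 / 0.046 = 0.63. Check: -0.40 + 0.058 × 0.63 - 0.104 × 0.63 = -0.429.
- Equal rates (5.8% v 5.9%): -0.396, about no bias.

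Averaged over visits, more terminations in GMI (27% to 28% v 16% to 17% by month 6) give -0.44 to -0.45. Rates that differ by arm but are unrelated to use give -0.40. With a true effect of zero, fewer terminations in GMI give about +0.02 and more in GMI about -0.04.

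**3. Size.** Assumptions: baseline plus months 1, 3 and 6; SD 1; correlation 0.5; true difference -0.40; Gaussian maximum likelihood under MAR; termination when current use exceeds the control 98th, 95th or 90th percentile (2%, 5% or 10% of controls per visit interval), with the same threshold in both arms.

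| Controls per interval | Terminated by month 6, CT v GMI | Of 93 per arm | Average, all unrecorded | Average, half recorded first |
|---|---|---|---|---|
| 2% | 5.1% v 1.9% | 5 v 2 | -0.375 | -0.387 |
| 5% | 11.8% v 5.2% | 11 v 5 | -0.348 | -0.375 |
| 10% | 21.8% v 11.0% | 20 v 10 | -0.316 | -0.362 |

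Repeat runs agree within 0.005. If every trigger is recorded at a completed visit first, the estimate is -0.40. A soft trigger, all unrecorded, gives -0.394, -0.387 and -0.377.

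**4. Month 1.** The first interval runs about 3 weeks (week 1 to 4), the others 8 and 12. With risk proportional to interval length, the month-1 estimate is -0.39, -0.375 and -0.36 (all unrecorded), or -0.40, -0.39 and -0.38 (half recorded).

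**5. Pilot-scaled check.** C2a reports detoxification re-admission within 3 months of 6.8% (GMI) and 25.6% (standard treatment). At a quarter, half and all of those rates, a soft trigger gives -0.380, -0.358 and -0.317 unrecorded, and -0.391, -0.381 and -0.363 with half recorded.

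**6. Power.** At 65 per arm with the SE re-estimated by simulation, 79.2% without termination becomes 76.9%, 75.3% and 71.0% (the sharp threshold of step 3, all unrecorded), or 79.0%, 78.6% and 76.2% (half recorded).

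**The case against.** **The text may not stop assessments.** The wording in (c) can mean the treatment only, and the follow-up phrase is tied to referral. In the pilot, re-admission and 3-month binge-drinking percentages fit the same denominators (3/44 and 15/44; 11/43 and 24/43), which suggests, without proving, that re-admitted patients were still interviewed. This stands as a reason not to read the rule as certainly ending follow-up. It leaves staff free to apply it either way.

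**Bias toward zero is not a given.** A reader might infer that any difference by arm dilutes the effect. It does not: GMI encourages medication and treatment attendance, so trigger (c) could be met more often there. In the housed subset of the preceding VA trial, all interviews were completed by 13 of 15 in GMI and 8 of 8 in TAU; this is small and not specific to termination, but points the other way. This stands.

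**Safeguards exist.** A reader might infer that no departure from MAR is examined. C12a has a missing-equals-use worst case whose worked example is a drinking-day count, and it intends to correct for informative drop-out. That is partial cover: no method is named for standard drinks, peak drinks or other counts, and the per-protocol set requires complete measurements, so it excludes the same people. The sample-size inflation in C11 does not remove bias, and the VINCI data in C12e could cover utilization but not drinking.

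**All-unrecorded is the harsh case.** Follow-up visits screen with TLFB and BSI, so many triggers may be recorded first. This stands, and it is why the half-recorded figures are shown alongside.

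**Conclusion.** The concern holds as a conditional one. As written, the rule can remove later outcomes because a primary outcome worsened, and the MAR model does not correct for triggers that no visit recorded. Bias needs four things together: assessments stop, triggers go unrecorded, frequency differs by arm, and termination is tied to use. It runs toward zero if CT has more terminations (the natural case for trigger (a) if GMI works) and away from zero if GMI has more.

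Over the assumed rates with more in CT, a true -0.40 SD averages about -0.38 to -0.31 with all triggers unrecorded and -0.39 to -0.36 with half recorded. Month 1 is affected only by terminations before that visit. The results rest on assumed rates and on reading 0.4 drinks as 0.40 SD; treatment engagement is not quantified.

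A reader might take the full pilot rates with a sharp trigger, all unrecorded, and conclude that the effect nearly halves (-0.22). The documents do not support that: those were psychiatric inpatients, and this trial excludes people with unstable conditions likely to need hospitalization. Nor do they support a claim that the month-1 result is seriously compromised. This is a modest, avoidable weakness worth correcting.

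**What to change.** Keep the clinical criteria and referrals unchanged. In section 2B, state that meeting a trigger ends study sessions, including the booster, and nothing else. The participant remains in the ITT set, is invited to the month 1, 3 and 6 assessments when clinically safe, and has CPRS encounters counted, unless consent is withdrawn.

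Record the date and trigger of each termination by arm, and whether a completed visit had already recorded it.

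In C12a, add one delta-adjusted sensitivity analysis for outcomes the worst case does not cover: values after termination set 0 to 1 SD worse than the MAR prediction, applied by arm, with a stated rate multiplier for counts. In the all-unrecorded simulations the shift that restored -0.40 was about 0.5 SD with the soft trigger and 1.0 to 1.1 SD with the sharp one, so extend the range slightly if the sharp case is to be spanned.

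The cost is a protocol clarification and a short analysis paragraph; the visits are already scheduled and reasons for missing data are already to be documented. Some follow-ups will be harder to arrange, or must be postponed, during an inpatient stay or crisis.
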